#### 11.4      **Electrocardiogram (ECG)**

Descriptive statistics for ECG variables (eg, heart rate, RR interval, PR interval, QRS interval, QT interval, and QTc interval) and their changes from baseline at each assessment time point will be presented. QTc interval will be calculated using both Bazett ( $QTcB=QT/(RR)^{1/2}$ ) and Fridericia ( $QTcF=QT/(RR)^{1/3}$ ) corrections; and if RR is not available, it will be replaced with 60/heart rate in the correction formula. Electrocardiogram interpretation will be summarized by assessment time point for all scheduled assessments. A shift table from baseline to each assessment time point for qualitative ECG results will be presented.

For the ECG interval parameters, baseline is defined as the average of the triplicate ECG measurements obtained at the baseline visit (predose on Day 1) prior to the administration of the investigational product. For the ECG interpretation, baseline will be the ECG with the worst interpretation obtained at the baseline visit (predose on Day 1), providing this is prior to the administration of the investigational product. The ECG interpretation of normal will be considered better than abnormal, and not clinically significant abnormal will be considered better than clinically significant abnormal.

Electrocardiogram variable values will be considered PCI if they meet or exceed the upper limit values listed in [Table 9](#). The number and percentage of subjects with post-baseline PCI values will be tabulated. The percentages will be calculated relative to the number of subjects with available non-PCI baseline and at least 1 post-baseline assessment. The numerator is the total number of subjects with at least 1 PCI post-baseline ECG value. A listing of all subjects with post-baseline PCI value will be provided including the subject number, baseline, and post-baseline PCI values.

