7.2.2.7 Electrocardiogram

Twelve-lead ECGs will be performed at the times specified in [Table 1](#) (rich PK sample subset) and [Table 2](#) (sparse PK sample subset). All ECGs will be performed after 5 minutes of rest using equipment approved by the central ECG laboratory and will be sent to the central ECG provider according to the instructions in the ECG manual provided by the ECG laboratory.

Additionally, ECGs will be performed in triplicate (with a 2 to 5 minute gap between traces) at screening. The subject should be asked to remove all clothing that covers the locations of lead placement. The subject must be resting in the supine position for at least 5 minutes prior to collecting the ECG.

In some cases, it may be appropriate to repeat abnormal ECGs to rule out improper lead placement as contributing to the ECG abnormality. It is important that leads are placed in approximately the same positions each time in order to achieve precise ECG recordings. A single recording, including a 10 second rhythm strip, will be obtained for all assessments after the baseline. The time and date of each ECG obtained will be recorded on the CRF. A trace ECG recording will be printed and placed in the site's study file for every ECG taken.

The initial interpretation of the ECG, normal or abnormal and clinical significance, will be performed by the Investigator immediately after collection to ensure the safety of each subject. An ECG tracing will then be evaluated by a pediatric cardiologist at a central ECG reading vendor and returned to the site with a determination of normal or abnormal. Upon review of the report from this vendor, the investigator will re-evaluate the clinical significance of the ECG while taking into consideration all other safety data available for the subject.

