Although a central ECG reader is being used for this study, the eligibility of the subject is based on the investigator's assessment of the ECG. If abnormal and significant results are observed following assessment by the central reader, the investigator, in consultation with the appointed CRO Medical Monitor, confirms subject eligibility to continue. All ECGs transmitted to the central ECG reader will be analyzed. If the central ECG reader receives multiple ECGs, the first readable ECGs will be analyzed as the scheduled ECG. Every ECG transmitted to the central ECG reader will have corresponding source document data collected. No ECG should be deleted by study site personnel. All ECGs must be transmitted to the central provider regardless of quality, results, or number of ECGs taken at a respective visit.

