**Table 9: Criteria for Potentially Clinically Important ECG Values**

ECG Parameter	Unit	Observed Value		Change from Baseline	
		Lower Limit	Higher Limit	Lower Limit	Higher Limit
ECG Result	-	-	Abnormal (core lab) and clinically significant from investigator	-	-
Heart Rate	beats/minute	<55	>130	Decrease >15	Increase >15
PR Interval	msec	-	≥200	-	-
QT Interval	msec	-	≥440	-	≥30 and <60 ≥60
QTcF Interval	msec	-	≥440 and <480 ≥480 and <500 ≥500	-	≥30 and <60 ≥60
QTcB Interval	msec	-	≥440 and <480 ≥480 and <500 ≥500	-	≥30 and <60 ≥60
QRS Interval	msec	-	≥90	-	-
Rhythm	-	-	Any rhythm other than sinus rhythm ECG evaluation –abnormal rhythm 
 
• Complete Heart Block
 
• Tachycardia
 
• Bradycardia
 
• Wandering Atrial Pacemaker
 
• Ectopic Atrial Rhythm
 
• Atrial Fibrillation
 
• Atrial Flutter
 
• Multifocal Atrial Tachycardia
 
• Supraventricular Tachycardia
 
• Atrial Bigeminy
 
• Ventricular Bigeminy
 
• Atrial Couplets
 
• Ventricular Couplets
 
• Ventricular Tachycardia
 
• Torsade des Pointes
 
• Ventricular Fibrillation
 
• Junctional Rhythm
 
• Idioventricular Rhythm
 
• Escape Beat
 
• Atrial Pacemaker
 
	-	-

Additionally, a summary table showing the number and percentage of subjects with the Central Reader's assessment of the ECG result as normal, abnormal or unable to evaluate, and the investigator's assessment of abnormal ECG results as not clinically significant or clinically significant at each time point and at the FoTA will be produced. A shift table showing the change in evaluation from baseline to the FoTA by treatment group will also be produced.

All ECG data will be listed for the safety set. Listings of ECG data including the central reader's assessment and investigator's interpretation by individual subject will also be produced.

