### **18.4 Repeated or Unscheduled Assessments of Safety Parameters**

If a subject has repeated or unscheduled assessments before the start of investigational product, then the results from the final assessment made prior to the start of investigational product will be used as baseline. For the ECG interval parameters, this will be the average of the triplicate ECG measurements obtained at the baseline visit (predose on Day 1) prior to the first dose of the investigational product. For the ECG interpretation, baseline will be the ECG with the worst interpretation obtained at the baseline visit (predose on Day 1), providing this is prior to the first dose of the investigational product.

If a subject has repeated assessments at any post-baseline assessment time point, the first recorded assessment will be assigned to the assessment time point for generating descriptive statistics. For vital signs (sitting systolic blood pressure, diastolic blood pressure, and pulse), this will be the average of the 3 measurements from the first recorded assessment. For the ECG interpretation, if there are multiple assessments at any assessment time point, the worst interpretation will be used for generating descriptive statistics.

If end of study assessments are repeated or unscheduled, the last post-baseline assessment will be used as the end of study assessment for generating descriptive statistics. For vital signs (sitting systolic and diastolic blood pressure and pulse), this will be the average of the 3 measurements from the last post-baseline assessment.

However, all post-baseline assessments will be used for PCI value determination and all assessments, including unscheduled and repeated assessments, will be presented in the data listings.

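### If the Day 1 ECG is triplicate, as the SAP states, the qualitative ECG shift tables compare the worst of three baseline tracings with one later tracing and tilt toward apparent improvement

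*SAP*

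**What the plan says.** **Baseline.** SAP 11.4 defines the baseline for ECG intervals as "the average of the triplicate ECG measurements obtained at the baseline visit (predose on Day 1"). For the qualitative result it says: "For the ECG interpretation, baseline will be the ECG with the worst interpretation obtained at the baseline visit (predose on Day 1"). SAP 18.4 repeats both rules.

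**After baseline.** Protocol 7.2.2.7 says: "A single recording, including a 10 second rhythm strip, will be obtained for all assessments after the baseline". SAP 18.4 adds, for the interpretation: "if there are multiple assessments at any assessment time point, the worst interpretation will be used for generating descriptive statistics".

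**Where the triplicate is scheduled.** Protocol 7.2.2.7 says: "ECGs will be performed in triplicate (with a 2 to 5 minute gap between traces) at screening". It does not name Day 1 predose, although the schedule tables do place an ECG there.

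**Outputs that use the comparison.** SAP 11.4 says: "A shift table from baseline to each assessment time point for qualitative ECG results will be presented". After Table 9 it adds: "A shift table showing the change in evaluation from baseline to the FoTA by treatment group will also be produced".

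**The concern.** A shift table is meant to show which abnormalities are new since baseline. It does so fairly only if each child is classified in the same way before and after drug. Taking the worst of several tracings raises the chance of an abnormal classification. If this happens with three tracings before drug and one after, the baseline looks worse than later visits for reasons unrelated to treatment. Some children whose post-dose ECG would have counted as newly abnormal are already abnormal at baseline, and others appear to recover.

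The normal-to-abnormal cell is the safety signal in this table. The study has one arm, so no control group would reveal the artefact, and safety of a stimulant in 4- to 5-year-olds is part of the primary objective.

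**Working it through.** The documents give no expected figure for the ECG shift tables, so there is nothing to reproduce. The check asks what the tables would show with no drug effect.

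**Inputs from the documents**
- Baseline tracings: 3, worst taken (SAP 11.4 and 18.4).
- Tracings at each later scheduled assessment: 1 (Protocol 7.2.2.7).
- Children: 10 + 10 = 20 expected completers (SAP 2.5).

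**Assumed inputs, absent from the documents**
- *p*, the chance that a single tracing reads abnormal: 0.05 to 0.20 shown.
- ρ, the correlation of reads within a child: 0 to 0.8.

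**Formulas.** Let q(j) be the probability that j tracings from one child are all normal.
- Independent reads: q(j) = (1 − p)^j.
- Correlated reads (beta-binomial): let s = (1 − ρ)/ρ and b = (1 − p)s. Then q(j) is the product of (b + i)/(s + i) for i = 0 to j − 1.
- Worst of 3 against one: improved = q(1) − q(4); worsened = q(3) − q(4).
- One against one: q(1) − q(2) in each direction.

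**Independent reads, p = 0.10**
- Baseline abnormal = 1 − 0.9³ = 27.1%, against 10% later.
- Improved = 0.271 × 0.9 = 24.4%.
- Worsened = 0.729 × 0.1 = 7.3%.
- One against one = 0.1 × 0.9 = 9.0% each way.

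**Correlation 0.5, p = 0.10** (s = 1, b = 0.9)
- q(1) = 0.900; q(2) = 0.900 × 1.9/2 = 0.855; q(3) = 0.855 × 2.9/3 = 0.8265; q(4) = 0.8265 × 3.9/4 = 0.8058.
- Improved = 0.900 − 0.8058 = 9.4%.
- Worsened = 0.8265 − 0.8058 = 2.1%.
- One against one = 0.900 − 0.855 = 4.5% each way.

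| p | ρ | Baseline abnormal, worst of 3 | Improved | Worsened | One against one, each way | Of 20 children: improved / worsened (one against one, each) |
|---|---|---|---|---|---|---|
| 0.05 | 0 | 14.3% | 13.5% | 4.3% | 4.8% | 2.7 / 0.9 (1.0) |
| 0.10 | 0 | 27.1% | 24.4% | 7.3% | 9.0% | 4.9 / 1.5 (1.8) |
| 0.10 | 0.3 | 20.8% | 14.3% | 3.5% | 6.3% | 2.9 / 0.7 (1.3) |
| 0.10 | 0.5 | 17.4% | 9.4% | 2.1% | 4.5% | 1.9 / 0.4 (0.9) |
| 0.10 | 0.8 | 12.8% | 3.5% | 0.7% | 1.8% | 0.7 / 0.1 (0.4) |
| 0.20 | 0 | 48.8% | 39.0% | 10.2% | 16.0% | 7.8 / 2.0 (3.2) |
| 0.20 | 0.5 | 32.8% | 16.2% | 3.4% | 8.0% | 3.2 / 0.7 (1.6) |

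In these rows apparent improvement is about 3 to 5 times apparent worsening. At p = 0.10 the worsened cell loses 19% of its content with independent reads (9.0% to 7.3%) and about half at correlation 0.5 (4.5% to 2.1%). The relative loss grows with correlation, while the number of children affected becomes small.

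**Two checks.** With equal numbers of tracings the null shifts balance: worst of 3 against worst of 3 at p = 0.10 gives 19.8% each way with independent reads and 5.0% each way at correlation 0.5. With one tracing on Day 1, the worst of one is that tracing and the bias is zero.

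**The case against.** The other side has a substantial case.

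- **The SAP's rule is symmetric in form.** A reader might infer that the SAP prescribes the worst tracing before dosing and a single tracing after. It does not: 18.4 also takes the worst when several post-baseline tracings exist. This stands. The imbalance comes from the protocol's schedule, because on the normal schedule there is only one later tracing to choose from.
- **The premise is unsettled.** The rule reaches only Day 1 predose tracings, and the protocol names screening for the triplicate. This stands as a condition. Against it, the SAP states the Day 1 triplicate in two sections, and the protocol limits single recordings to assessments after the baseline.
- **A departure from the protocol might be inferred** from Protocol 7.2.2.7: "If the central ECG reader receives multiple ECGs, the first readable ECGs will be analyzed as the scheduled ECG". That sentence tells the central reader how to handle multiple transmissions, and it follows a statement that all transmitted ECGs are analyzed. It does not say which tracing of a planned triplicate gives the baseline category, so it does not establish a conflict.
- **It might be inferred that new abnormalities are hidden.** They are not. The summaries by time point, the central-reader and investigator table, the potentially clinically important (PCI) table and the listings still show them. The PCI denominator requires a non-PCI baseline, but the numerator as worded counts every child with a post-baseline PCI value. What these outputs lack is the direct before-and-after classification of a shift table.
- **The size is assumed.** One correlation is used for tracings minutes apart and weeks apart. Higher agreement within a visit would shrink the effect. Exclusion criterion 11 also removes children with clinically significant ECG abnormalities at screening. Both points stand.

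**Conclusion.** The concern holds conditionally. If Day 1 is triplicate, as the SAP states, and later assessments are single, as the protocol schedules, the shift tables to each time point and to the final on-treatment assessment (FoTA) favour improvement with no drug effect.

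The direction does not depend on the assumed inputs unless within-visit tracings agree perfectly; the size does. At 10% abnormal per tracing and correlation 0.5, about half a child in 20 is lost from the normal-to-abnormal cell (0.9 to 0.4), and about one extra child appears to improve (0.9 to 1.9). When tracings agree closely the effect is under one child.

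This is a modest defect in two descriptive tables and does not undermine the ECG safety evaluation as a whole. It is worth correcting because the study is small and single-arm, and the correction is only wording.

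**What to change.** 1. Reconcile Protocol 7.2.2.7 with SAP 11.4 and 18.4 on which visit supplies the triplicate ECG.
2. For the shift tables, use the same selection rule and the same number of tracings on both sides, replacing the worst-of rule in both 11.4 and 18.4. Possible wording: *For the qualitative ECG shift tables, the first readable scheduled tracing will be used at the baseline visit and at each post-baseline time point, including the time point that supplies the FoTA.* Changing only the baseline rule would leave repeat post-dose tracings under worst-of and could tilt the tables the other way.
3. Keep the triplicate mean for interval parameters, keep all post-baseline tracings for PCI determination, and list every tracing.
4. State in the shift-table footnote how many tracings each side uses.

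The cost is SAP wording and a footnote, with no new data. The small downside is that an abnormality seen only on a repeat tracing would not enter the shift table. It would appear in the listings and, where it meets a PCI criterion, in the PCI table.

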## 11.2 Clinical Laboratory Variables

Descriptive statistics for clinical laboratory values (in SI units) and changes from baseline to Week 4/ET as well as shift tables from baseline to Week 4/ET for quantitative variables will be presented for the following clinical laboratory variables.

**Hematology** Hemoglobin, hematocrit, red blood cells, platelet count, white blood cell count – total and differential, total neutrophils (absolute and relative), eosinophils (absolute and relative), monocytes (absolute and relative), basophils (absolute and relative), and lymphocytes (absolute and relative).

**Biochemistry** Sodium, potassium, glucose, blood urea nitrogen, creatinine, calcium, chloride, thyroid-stimulating hormone, thyroxine, tri-iodothyronine, phosphorus, total protein, total CO2 (bicarbonate), albumin, aspartate transaminase, alanine transaminase, gamma glutamyl transferase, alkaline phosphatase, total bilirubin, and uric acid.

**Urinalysis** pH, glucose, protein, blood, ketones, bilirubin, nitrites, leukocyte esterase, and specific gravity.

Microscopic examination will be conducted if protein and/or blood is/are detected during urinalysis. At a minimum the microscopic examination will consist of red blood cells, white blood cells, casts, and bacteria.

Clinical laboratory test values are potentially clinically important (PCI) if they meet either the low or high PCI criteria listed in [Table 5](#). The number and percentage of subjects with post-baseline PCI values will be tabulated. The percentages will be calculated relative to the number of subjects with available baseline values and at least 1 post-baseline assessment. The numerator is the total number of subjects with at least 1 post-baseline PCI value. A supportive listing of subjects with post-baseline PCI values will be provided including the subject number, baseline, and post-baseline values.

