**Table 6: Criteria for Potentially Clinically Significant Vital Signs**

Vital Sign Parameter	Flag	Criteria a	
		Observed Value	Change from Baseline
Sitting Systolic blood pressure (mmHg)	High	≥120	Increase of >10
	Low	<75	Decrease of >10
Sitting Diastolic blood pressure (mmHg)	High	≥85	Increase of >10
	Low	<40	Decrease of >10
Pulse rate (beats per minute)	High	≥130	Increase of >15
	Low	≤55	Decrease of >15
Weight (kg)	High	-	Increase of ≥7%
	Low	-	Decrease of ≥7%
Temperature (deg. C)	High	>39	-
	Low	<35	-
BMI (kg/m  )	High	>95th percentile for age and sex	-
	Low	<5th percentile for age and sex	-

a A post-baseline value is considered as a PCI value if its meets either the criteria for observed value or the criteria for change from baseline.

Measurements of oral or tympanic temperature, sitting respiratory rate will be performed at the screening visit and ET visit only.

Pulse rate (beats per minute) will be considered abnormal if a value is lower than the 1st percentile or higher than the 99th percentile cut-off values listed in [Table 7](#).

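### SAP 11.4 applies only the upper limits of Table 9 to ECG values, so the table's two lower-limit heart-rate criteria are never used in the ECG PCI count as written

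*SAP*

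**What the plan says.** The counting rule is in SAP 11.4: "Electrocardiogram variable values will be considered PCI if they meet or exceed the upper limit values listed in" Table 9. No clause covers lower limits.

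Table 9 is titled "Criteria for Potentially Clinically Important ECG Values". It has a lower and a higher column for the observed value, and the same pair for change from baseline. One row fills all four cells: "Heart Rate beats/minute <55 >130 Decrease >15 Increase >15". Every other row has a dash in both lower columns.

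The rule feeds both parts of the reported percentage. For the numerator: "The numerator is the total number of subjects with at least 1 PCI post-baseline ECG value". The denominator is restricted to subjects with an "available non-PCI baseline and at least 1 post-baseline assessment". The outputs concerned are Table 14.3.6.4 and Listing 16.2.8.3.2 in SAP section 20.

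For comparison, SAP 11.2 flags laboratory values "if they meet either the low or high PCI criteria listed in" its own table, which is two-sided wording.

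**The concern.** A programmer who follows 11.4 would flag high heart rates and rises and would ignore the two low-side limits that Table 9 prints as PCI criteria. A programmer who follows Table 9 would flag both sides. The same data could then give different counts, and both readings can be defended from the SAP. Safety is part of the primary objective, and with about 24 children one child moves a percentage by about 4 points (1/24 = 4.2%). A count that depends on which half of a section was read should be settled before the data are seen.

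**Working it through.** There is no sample size, power or error-rate figure to reproduce. The check sets the rule beside the table.

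**Heart-rate limits, one by one**

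| Limit in Table 9 | Column | Applied by the 11.4 text? |
|---|---|---|
| <55 observed | lower | no |
| >130 observed | higher | yes, but 130 itself is included |
| Decrease >15 | lower | no |
| Increase >15 | higher | yes, but a rise of exactly 15 is included |

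Two of the four limits are not applied. In the interval rows (PR, QRS, QT, QTcF, QTcB) the upper cut-offs are written as at-or-above, so text and table agree there. The mismatch is confined to heart rate.

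**Numerator example (assumed values).** Baseline 70, post-baseline 50. By Table 9, 50 is below 55 and the fall is 70 − 50 = 20, which is more than 15. Both low-side limits are met, so the value is PCI however the observed and change criteria are joined. By the text, 50 does not reach 130 and there is no rise, so it is not PCI.

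**Denominator.** A child with a baseline rate below 55 has a non-PCI baseline under the text and stays in. Under Table 9 the baseline is PCI and the child drops out.

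**Does other text settle it?** SAP 18.4 says all post-baseline assessments are used for PCI determination, but not which limits apply. SAP section 17 does not mention the point.

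**The joining rule.** SAP 11.4 does not say whether observed-value and change criteria are alternatives or must both be met. Take an assumed fall from 110 to 90: the change is −20 and the observed rate is not below 55. By Table 9 this is PCI under 'or' and not PCI under 'and'. The vital-sign section offers no model, because the text of SAP 11.3 requires both conditions and the footnote to Table 6 accepts either.

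**Size, as illustration only.** The documents give no SD for the change in heart rate. Assumptions:
- The within-child SD of change is 8 to 12 bpm. This has no source in the documents.
- The mean rise is 3 to 6 bpm (protocol 1.2, from a programme in ages 6 to 55).
- The criteria are joined by 'or'.
- There are 12 children per portion and readings are independent.

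Per reading, P(fall >15) is:
- upper end: z = (−15 − 3)/12 = −1.50, giving 6.7%
- lower end: z = (−15 − 6)/8 = −2.63, giving 0.4%

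The schedules give 5 post-baseline ECGs in the rich portion (Day 1 of Weeks 2 and 3, two on Day 7 of Week 4, and Day 9). They give 3 in the sparse portion (Day 1 of Weeks 2 and 3, and Day 8). The expected number of children with at least one such fall is:
- upper end: 12 × (1 − 0.933⁵) + 12 × (1 − 0.933³) ≈ 3.5 + 2.3 ≈ 6
- lower end: 12 × (1 − 0.9957⁵) + 12 × (1 − 0.9957³) ≈ 0.4

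Correlated readings would lower these figures. The limit of 55 should rarely be reached, since SAP Table 7 puts the 1st percentile of pulse at 69 (boys) and 70 (girls). Under 'and' the loss would therefore be close to nil.

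**The case against.** The case for leaving this alone is that it is a wording slip with little consequence.

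- Table 9 plainly intends its lower limits, and SAP section 1 says output specifications are in a separate document, where the slip may be put right. This is fair as to intent. But that document is not part of the plan, and the only counting rule in the SAP is one-sided.
- A reader might infer that every slow or falling heart rate vanishes from the ECG PCI outputs. The documents do not support that. Bradycardia is listed in the Rhythm row under the higher limit. An ECG called abnormal by the central laboratory and clinically significant by the investigator sits in the same column. Both still count under the literal text. What is lost is a numeric rate below 55, or a fall of more than 15, without such a finding.
- A reader might also infer that a safety signal is lost. It is not. Heart rate and its change are summarised at each time point, all ECG data are listed, and pulse below the 1st percentile is tabulated and listed under SAP 11.3. Table 6 also flags low pulse at "≤55 Decrease of >15", although the both-or-either conflict makes that flag an uncertain backstop.
- Protocol 1.2 reports mean rises in heart rate, and the high side is counted. This lowers the stakes but does not reconcile text and table.
- The boundary conflict matters only at exactly 130 or exactly 15. That is true, and the same edit removes it.

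**Conclusion.** The inconsistency is real, and nothing else in the SAP resolves it. As written, two of the four heart-rate limits in Table 9 are never applied in Table 14.3.6.4 or Listing 16.2.8.3.2, and the lower observed limit is not used to define the non-PCI baseline. This conclusion rests on the wording alone and needs no numerical assumption.

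Its reach is narrow: one parameter in one descriptive safety count, with the underlying data still reported elsewhere. The range of about 0.4 to 6 children depends on an assumed SD, on 'or' joining and on independent readings. It shows only that the number could be nil or more than nil, and should not be quoted as an expected error. The documents also do not show that 'or' is the intended joining rule, so that choice belongs to the sponsor. The point is a text-to-table inconsistency that should be corrected before database lock.

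**What to change.** Replace the sentence in SAP 11.4 with: *ECG values will be considered PCI if they meet the lower- or higher-limit criteria listed in Table 9, using the inequality signs shown there.* This brings in the two low-side limits, removes the conflict at 130 and 15, and changes no threshold.

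As a separate item, have the sponsor state for Table 9 whether observed-value and change-from-baseline criteria are joined by 'and' or 'or', and reconcile the SAP 11.3 text with the Table 6 footnote at the same time.

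The cost is one replaced sentence and one added clarification in the SAP, with a check that the programming specifications match. No data collection or protocol text changes.
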